6.0 Procedures Involved*

6.1 To test the hypothesis, this study will utilize a randomized, double-blind, placebo-controlled between-subject design to examine the effects of CHO and CHO-P supplementation on short-term recovery following aerobic interval exercise and time to exhaustion testing in MCA's. After completing the informed consent and screening process (Visit #1), each participant will be assessed for their anthropometric measures as well as body composition and will complete a GXT to volitional exhaustion on a cycle ergometer to determine VO₂peak. Participants will also be provided with the option to return to the lab on a separate date for the GXT and VO₂peak testing. Forty-eight to 72 hours after Visit #1, or VO₂peak testing, participants will return to the lab for familiarization with the INT exercise protocol and TTE (Visit #2). Within five to nine days after familiarization (Visit #2), participants will return to the lab for Visit #3 to complete INT exercise and TTE, a 2-hour passive recovery period including the consumption of one of three treatments (CHO, CHO-P, PLA), followed by repeated INT exercise and TTE, HRV and SR determination. Participants will also complete the Nutritional Recovery Practices, Knowledge, and Beliefs of Australian Triathletes survey during the 2-hour recovery period. Participants will be asked to complete the ASA24®, an automated self-administered 24-hour dietary assessment tool during the 5-9-day period between familiarization (Visit #2) and the experimental protocol (Visit #3).

Testing Procedures.

- Participants will report to the testing location on 3 separate occasions.
- Visit #1: The study will be explained to the participant by the investigators. Participants will be asked to provide their written, informed consent. The participants will then be asked to complete the American College of Sports Medicine Exercise Preparticipation Health Screening Questionnaire for Exercise Professionals (PHSQEP), Physical Activity Readiness Questionnaire for Everyone (PAR-Q+), and Medical Health and Activity Questionnaire.

Following the written consent and screening process, anthropometrics and body composition will be measured, and the VO₂peak test outlined in section 6.3 will be completed. Following informed consent, screening, and anthropometrics and body composition, if necessary (i.e., due to time constraints), participants may choose to return to the lab on a separate occasion for VO₂peak testing.

- Visit #2: Participants will report to the testing location for familiarization to the testing protocols. Based on VO₂peak data obtained during Visit #1, participants will perform the INT and TTE protocol outlined in section 6.4 to familiarize them with the protocol for the experimental trial (Visit #3), and teach them how to respond to the rating of perceived exertion RPE measures.
- Visit #3: To ensure participants are hydrated prior to the start of testing, they will be asked to consume 500 ml of water 2 hours before their arrival to the laboratory for testing (Moreno et al. 2013; Vanderlei et al. 2015). Participants will complete a warm-up followed by the INT and TTE protocol, as outlined in section 6.4. Immediately following the INT and TTE testing, the participant will be given an isocaloric CHO (1.2 g/kg of bw), CHO-P (0.8 g/kg bw CHO + 0.4 g/kg bw protein), or PLA beverage that have a similar appearance and taste and will be blinded to the contents. Participants will rest for two hours and then repeat the INT and TTE testing (6.4). Participants will be weighed in their cycling bib shorts immediately before and after the first and second bouts of INT exercise and TTE testing. Sweat rate will be determined based on the difference between pre-and post-weight changes for each bout of exercise, the amount of fluid consumed during the recovery period, and total exercise time in minutes (Casa 2019). Participants will also be asked to report total sleep in number of hours and minutes for the night prior to testing. Immediately upon completion of the second exercise bout, participants will rest for an additional 30 minutes for HRV recording. Completion of Visit #3 will conclude all required testing.

6.2 Anthropometric measurements:

- Participants will be assessed for body weight, height, and body composition.

- Height will be assessed using a stadiometer (Health-o-meter Professional Patient Weighing Scale, Model 500 KL, Pelstar, Alsip, IL, USA), and body composition and weight will be assessed using Bioelectrical Impedance Analysis (InBody 770, Biospace Co, Ltd. Seoul, Korea). Participants will be asked to remove any jewelry, their footwear, including socks, and wear only light athletic attire. Then they will be asked to stand on a platform while holding two handles out to the side. They will hold this position as the bioelectrical impedance analysis sends a minute electrical current (that is safe and cannot be seen or felt) through the body, to determine body composition. There are no risks or discomforts associated with the use of bioelectrical impedance analysis. Participants should be two-hours fasted for this assessment.

6.3 Determination of VO₂peak

- All participants will perform a graded exercise test (GXT) to volitional exhaustion on a cycle ergometer (Lode, Corival cpet, Groningen, The Netherlands) to determine VO₂peak and peak power output. Prior to testing, each participant will be provided with a Polar heart rate monitor (chest strap and sensor; Polar H10, Polar Electro Oy, Kempele, Finland) to record heart rate. Participants will be asked to place the heart rate monitor just below the sternum. Participants will complete a five-minute warm-up on the cycle ergometer at a self-selected intensity and cadence. The test will consist of 2-minute stages, beginning at an initial workload of 50 watts (W), then 100W, then 150W followed by an increases of 30W every 2 minutes until the participants can no longer maintain 60 revolutions per minute (rpm) (Beltz et al. 2016; McCarthy and Spriet 2019). VO₂peak will be determined as the highest peak value achieved during the last completed stage of the test, and if it coincides with at least two of the following three parameters: heart rate (HR) within 10% of age-predicted maximal HR; respiratory exchange ratio (RER) of 1.15 or higher; a plateau in oxygen consumption despite an increase in exercise intensity. Open-circuit spirometry will be used to estimate VO₂peak (l·min⁻¹) with a calibrated metabolic cart (True One 2400® Metabolic Measurement System, Parvo-Medics Inc., Sandy, UT) by sampling and analyzing the breath-by-breath

expired gases. The metabolic cart software continuously records ventilation and expired gases, with averages every 15s, calculates VO_2 , and determines the VO_2peak value. The highest power output achieved will be recorded as peak power output (PPO) in watts.

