6.4 High-Intensity Aerobic Intervals and Time to Exhaustion

- All participants will warm-up on a cycle ergometer for 3-minutes at 50W, 2-minutes at 100W, and 1-minute at 75W followed by a 3-minute rest. Participants will then perform 5 x 4-minute high-intensity aerobic intervals at 70-80% of individual PPO, as determined by the familiarization trial. Two-minutes of low-intensity cycling at 50W will separate intervals. Immediately following the fifth interval, participants will cycle at a work rate (watts) that corresponds to 90% PPO until volitional exhaustion or when rpm falls below 60 for 10 seconds. Following the endurance trial (INT and TTE), participants will cycle with no resistance for 5 minutes to cool down. Revolutions per minute will be the only performance measure visible to participants, and minimal verbal encouragement will be provided throughout the aerobic intervals and time to exhaustion. Rating of perceived exertion (RPE) will be recorded using the Borg 10 scale during the last 30 seconds of each aerobic and rest interval and once immediately before completion of the TTE.

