10.0 Inclusion and Exclusion Criteria*

10.1 Individuals will be screened for eligibility using the American College of Sports Medicine Exercise Preparticipation Health Screening Questionnaire for Exercise Professionals (PHSQEP), Physical Activity Readiness Questionnaire for Everyone (PAR-Q+), and confidential Medical Health and Activity Questionnaire to determine the need for medical clearance from a health care professional. Participants presenting

any sign or symptoms suggestive of cardiovascular, metabolic, or renal disease will be asked to seek medical clearance in order to participate.

10.2 Inclusion Criteria.

- Men between the ages of 35 and 59 years
- Free of any physical limitations as determined by the Exercise Preparticipation Health Screening Questionnaire for Exercise Professionals (PHSQEP), and a Physical Activity Readiness Questionnaire for Everyone (PAR-Q+)
- Regularly engaged in endurance exercise (running, cycling, swimming) for a minimum of three years, a weekly training volume of 5-10 hours, and a maximal oxygen uptake of $45.00 \text{ ml}\cdot\text{kg}^{-1}\cdot\text{min}^{-1}$ or higher as determined by completion of $\text{VO}_{2\text{peak}}$ assessment (Visit #1).

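### Section 6.3 scores VO₂peak from the last completed stage only and gives peak power no completion or proration rule; both should be redefined, as separate points.

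*Combined protocol and SAP*

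**What the plan says.** All places are in the combined protocol and SAP.

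- **Section 6.3, test.** Two-minute stages at 50, 100 and 150 W, "followed by an increases of 30W every 2 minutes until the participants can no longer maintain 60 revolutions per minute".
- **Section 6.3, VO₂peak.** "VO₂peak will be determined as the highest peak value achieved during the last completed stage of the test", confirmed by at least two of three criteria, one of which is a plateau. The section then adds: "The metabolic cart software continuously records ventilation and expired gases, with averages every 15s", and says that the software determines the VO₂peak value.
- **Section 6.3, peak power.** "The highest power output achieved will be recorded as peak power output (PPO) in watts". Nothing is said about a stage that is started but not finished.
- **Section 6.4, loads.** The depleting exercise is "5 x 4-minute high-intensity aerobic intervals at 70-80% of individual PPO, as determined by the familiarization trial". For the TTE, participants "cycle at a work rate (watts) that corresponds to 90% PPO".
- **Sections 6.1 and 6.8.** Section 6.1 bases the Visit 2 exercise on VO₂peak data from Visit 1. Section 6.8 lists the TTE as performed at 90% of VO₂peak, not 90% of PPO.
- **Section 10.2, entry.** Maximal oxygen uptake must be 45.00 ml/kg/min "or higher as determined by completion of" the VO₂peak assessment.
- **Section 17.1, analysis.** One-way ANCOVA of posttest TTE with pretest TTE as covariate.

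**The concern.** The two numbers taken from the graded test do different jobs, and each has its own scoring problem.

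VO₂peak is a listed outcome and the physiological entry test. Confining it to the last completed stage discards the gas data from the unfinished stage, where uptake may have been highest. The error can only lower the recorded value, and it matters most for athletes close to 45.00.

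PPO sets the load for the intervals and the TTE. Without a rule for an unfinished stage, it moves in 30 W jumps, so the same nominal percentage is a different relative load for different athletes. That adds variation in depletion and in TTE that has nothing to do with the drink, in a trial that aims for 18 completers, 6 per group (17.2).

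**Working it through.** **The plan's own figures.** The documents give no figure for the error in PPO or VO₂peak. The only related design figure is N = 18 with power 0.90 and alpha 0.05 (17.2). No effect size is given, so it cannot be reproduced. Solved backwards with a noncentral F for three groups and one covariate (df 2 and 14, noncentrality f² × 18), it needs f = 0.94. The point here does not dispute N.

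**1. VO₂peak: the most that can be hidden**

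Assumed inputs, not in the documents: oxygen cost of cycling 9-11 ml/min per W; body mass 65-95 kg. Step size is 30 W (6.3).

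Upper bound = 30 × oxygen cost / body mass, for a nearly complete extra stage with uptake still rising in step with power:

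- lowest: 30 × 9 / 95 = 2.8 ml/kg/min
- middle: 30 × 10 / 75 = 4.0 ml/kg/min
- highest: 30 × 11 / 65 = 5.1 ml/kg/min

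Half a step gives 1.4 to 2.5. A plateau gives about zero. At the bound, an athlete with a true peak of up to 47.8-50.1 could be recorded below 45.00. Because two of three criteria suffice, a VO₂peak can be accepted without a plateau.

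**2. PPO: spread in relative TTE load**

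Yardstick: prorated power = last completed stage + 30 × t / 120, where t is seconds in the unfinished stage. Relative load = 0.90 × PPO / prorated power, with PPO read as the step reached.

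- Stop 10 s into 300 W: prorated 270 + 30 × 10/120 = 272.5 W; load 270 W; 270 / 272.5 = 99.1%.
- Stop 10 s into 270 W: prorated 242.5 W; load 243 W; 243 / 242.5 = 100.2%.
- Finish the 300 W stage: 270 / 300 = 90%.

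| Step reached | Stop at 1 s | Stop at 60 s | Stop at 119 s | SD (uniform t) |
|---|---|---|---|---|
| 270 W | 101.1% | 95.3% | 90.1% | 3.2 points |
| 300 W | 99.9% | 94.7% | 90.1% | 2.9 points |
| 360 W | 98.1% | 93.9% | 90.1% | 2.4 points |

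Near neighbours: one athlete stops at 119 s of 270 W (prorated 269.75 W), another at 1 s of 300 W (270.25 W). They differ by 0.5 W, yet their TTE loads are 0.9 × 270 = 243 W and 0.9 × 300 = 270 W.

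**3. Is the spread due to PPO and VO₂peak using different stages?**

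Suppose PPO also came from the last completed stage. For a failed stage of 300 W the load is 0.9 × 270 = 243 W, which is 243 / 270.25 = 89.9% down to 243 / 299.75 = 81.1% of prorated power (SD 2.6 points). The spread is about the same. It comes from unprorated 30 W steps, not from the mismatch between the two rules.

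**The case against.** The case for leaving this as a minor clarification has several sound parts.

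- **The mismatch is not the mechanism.** A reader might infer that loads are unequal because PPO and VO₂peak come from different stages. Section 6.4 takes its loads from PPO alone, and the third check above gives a similar spread with matched rules. This stands, so the two weaknesses are separate.
- **Step reached is a reading.** It is the natural sense of the PPO sentence, but the text does not spell it out. An undefined rule still needs defining, and the completed-stage alternative does no better.
- **No bias between drinks.** A reader might infer that the comparison is distorted. Drinks are randomized, and 6.4 applies the same loads in both bouts. Taking the pretest in 17.1 as bout 1, the covariate should absorb much of a scaling error shared by both bouts. What remains is imprecision. Its size after adjustment cannot be computed, because the documents give neither the relation of TTE to load nor the correlation between bouts.
- **Intervals.** The 70-80% range appears to be settled at familiarization, so an athlete with a high PPO could be placed lower. The documents do not support a claim that athletes will fail to finish the intervals. The TTE load has no such adjustment.
- **Extremes do not coincide.** The largest PPO inflation needs failure early in a stage; the largest hidden VO₂ needs failure late. Prorated power is also an assumed yardstick.
- **Exclusion.** A reader might infer that eligible athletes will be wrongly turned away. That requires uptake still rising, a true value within a few ml/kg/min above 45, and staff applying the completed-stage rule rather than the software's value. It is possible, not shown, and would cost recruits rather than validity.

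**Conclusion.** Both weaknesses hold, at modest size.

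1. The VO₂peak rule can under-read a listed outcome and the entry measure by at most about 3-5 ml/kg/min. This rests on the assumed oxygen cost and body mass and on uptake still rising; the loss is near zero at a plateau.
2. PPO has no completion or proration rule. With PPO read as the step reached, a nominal 90% is about 90-100% of prorated peak power at 270-300 W. The SD is about 2.4-3.2 points across 270-360 W if stopping times are uniform. This is avoidable variation between participants, reduced by an unknown but probably large amount by the covariate.

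Neither makes the drink comparison invalid. The changes are worth making because they are cheap. Separately, 6.1, 6.4 and 6.8 do not agree on whether PPO or VO₂peak sets the load.

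**What to change.** In 6.3:

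- **VO₂peak.** Define it as the highest 30-second value (two consecutive 15-second averages) anywhere in the test, including an unfinished final stage, subject to the same two-of-three criteria. Use it for the 45.00 threshold in 10.2, and state that it takes precedence over the value the software reports.
- **PPO.** Define it as watts of the last completed stage + step size × (seconds in the final stage / 120).

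Reconcile 6.1, 6.4 and 6.8 on the basis of the load. State in 6.4 whether the familiarization trial settles the percentage within 70-80% or PPO itself.

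**Cost.** This is wording, plus noting the time in the final stage; the 15-second averages already exist. A 30-second mean may read slightly lower than a single 15-second peak, if that is what is now used. Compared with step-reached scoring, prorating lowers the TTE load by 0.9 × 30 × (1 − t/120): up to 27 W, and 13.5 W on average if t is uniform. Section 17.2 says the pilot used the same 90% PPO test. If the pilot scored PPO by step, its loads differ from those the trial will use, which weakens its link to N = 18. Say so in 17.2.

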6.4 High-Intensity Aerobic Intervals and Time to Exhaustion

- All participants will warm-up on a cycle ergometer for 3-minutes at 50W, 2-minutes at 100W, and 1-minute at 75W followed by a 3-minute rest. Participants will then perform 5 x 4-minute high-intensity aerobic intervals at 70-80% of individual PPO, as determined by the familiarization trial. Two-minutes of low-intensity cycling at 50W will separate intervals. Immediately following the fifth interval, participants will cycle at a work rate (watts) that corresponds to 90% PPO until volitional exhaustion or when rpm falls below 60 for 10 seconds. Following the endurance trial (INT and TTE), participants will cycle with no resistance for 5 minutes to cool down. Revolutions per minute will be the only performance measure visible to participants, and minimal verbal encouragement will be provided throughout the aerobic intervals and time to exhaustion. Rating of perceived exertion (RPE) will be recorded using the Borg 10 scale during the last 30 seconds of each aerobic and rest interval and once immediately before completion of the TTE.

6.5 Recovery Slope of Heart Rate Variability

- R-R intervals recorded via the heart rate monitor and Elite HRV will be downloaded and analyzed using a laptop with commercially available HRV analysis software (Kempele, Finland; Kubios HRV Analysis v 3.3, Kuopio, Finland). R-R interval series will be filtered using the software's automatic artifact correction to detect and replace artifacts from the normal sinus arrhythmia. Replaced R-R periods will not exceed 5% of total heartbeats. Each window will be analyzed for the time-domain values of root mean square of the successive differences of R-R intervals (RMSSD). RMSSD reactivation following exercise will be reported to behave linearly during the first 30-minutes post-exercise (Orellana et al. 2019). Therefore, RMSSD values will be recorded during the 90% TTE and then post-exercise every 5 min. Using

simple linear regression, a slope value for RMSSD values vs. time of recording (end of TTE, 5min, 10min, 15min, 20min, 25min, 30min) for each participant will be performed.

6.6 Dietary Analysis

- To understand if MCA are meeting carbohydrate and protein intake recommendations, participants will be asked to complete the ASA24®. The ASA24® is a validated, automated self-administered 24-hour dietary assessment tool developed by the National Cancer Institute (Bethesda, Maryland) (Park et al. 2018). Each participant will be instructed on the use of the ASA24® during Visit #1, either by a registered dietitian or a trained volunteer research assistant. Participants will be asked to report a typical daily intake for days that they train. Following completion of VO₂peak testing participants will be emailed a sample of a detailed diet recall and an individual username and password to access the ASA24® system. They will be asked to report a 24-hour intake that is typical for days that they train. The sample diet recall will demonstrate a level of detail that includes all foods and fluids consumed upon waking until bedtime, including foods and/or supplements consumed pre, during, and immediately post-exercise. Participants will be asked to complete the electronic diet recall during the 5-9-day period between familiarization (Visit #2) and the experimental protocol (Visit #3). After data collection, the dietary intake will also be analyzed for total energy (kilocalorie [kcal]) and macronutrient distribution (carbohydrate, protein, and fat). An Excel spreadsheet of each participant's macro-and micronutrient analysis will be downloaded from the ASA24® website.

6.7 Postexercise Nutritional Practices Survey

- The Nutritional Recovery Practices, Knowledge and Beliefs of Australian Triathletes survey is an instrument previously designed to assess knowledge of postexercise nutritional recommendations and recovery practices in endurance athletes (Doering et al. 2016b). Participants will complete the survey electronically during the 2-hour recovery period (Visit #3). Masters class athletes in this study will be asked to complete a series of 34 total questions assessing their postexercise nutrition knowledge and recovery

practices. Questions 1 through 10 will be omitted as the current study is not specific to triathletes.

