1.0 Study Summary

Study Title	Effects of Post-Exercise Recovery Drink Composition on Subsequent Performance in Masters Class Athletes
Study Design	Randomized, Double-blind, placebo-controlled between-subject
Primary Objective	The purpose of this study is to demonstrate that performance in a subsequent bout of high-intensity glycogen depleting exercise will not be significantly different regardless of post-exercise recovery drink (carbohydrate vs. carbohydrate and protein vs. placebo).
Secondary Objective(s)	Assess the level of sports nutrition knowledge and total daily carbohydrate and protein intake in a group of endurance-trained masters class athletes.
Research Intervention(s)/ Investigational Agent(s)	[name], MS, RDN [name] [name] [name] [name], BS
IND/IDE #	
Study Population	Male Athletes, Age 35-59 years
Sample Size	50
Study Duration for individual participants	14 days; 3-4 total visits
Study Specific Abbreviations/ Definitions	Graded Exercise Test (GXT), Maximal Oxygen Consumption (VO ₂ max), Plateau in Oxygen Uptake (VO ₂ peak), High-Intensity Aerobic Interval Exercise (INT), Time to Exhaustion (TTE), Heart Rate Variability (HRV), Sweat Rate (SR), Carbohydrate (CHO), Carbohydrate-Protein (CHO-P), Placebo (PLA), Masters Class Athletes (MCA's)

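### The recovery-nutrition survey falls between the masked drink and the second time-to-exhaustion test; giving it after all second-bout measurements would remove a plausible, unquantified expectancy cue at almost no cost.

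*Combined protocol and SAP*

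**What the plan says.** All references are to the combined protocol and SAP.

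- **Survey timing.** Section 6.7: "Participants will complete the survey electronically during the 2-hour recovery period (Visit #3"). Section 6.1 gives the same slot: "Participants will also complete the Nutritional Recovery Practices, Knowledge, and Beliefs of Australian Triathletes survey during the 2-hour recovery period".
- **Drink timing.** Section 6.1, Visit #3: "Immediately following the INT and TTE testing, the participant will be given an isocaloric CHO (1.2 g/kg of bw"), or one of the other two drinks.
- **Second bout.** Section 6.1, Visit #3: "Participants will rest for two hours and then repeat the INT and TTE testing (6.4"). A further 30 minutes of rest for HRV recording follows it.
- **Survey content.** Section 6.7 has participants "complete a series of 34 total questions assessing their postexercise nutrition knowledge and recovery" practices. The instrument's title also names beliefs. The items are not reproduced.
- **End of the TTE.** Section 6.4: riders continue "until volitional exhaustion or when rpm falls below 60 for 10 seconds".
- **Control of cues during the ride.** Section 6.4: "Revolutions per minute will be the only performance measure visible to participants, and minimal verbal encouragement will be provided".
- **Masking.** Sections 5.0 and 6.1 rely on drinks made to look and taste alike. One contains whey isolate at 0.4 g/kg, and the placebo is Gatorade G Zero. No question on which drink participants think they had, and no other check of masking, appears anywhere.

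**The concern.** Riding to exhaustion depends partly on how long the participant chooses to continue. Section 6.4 recognises this by hiding every performance measure except cadence and by keeping encouragement low. A questionnaire about recovery nutrition, taken after the drink and before the second ride, sits uneasily with that control. It may lead participants to think about what they drank and what it ought to do for them.

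The outcome exposed is the one that matters most. No endpoint is formally labelled primary. However, the primary objective in Section 1.0 is about whether "performance in a subsequent bout of high-intensity glycogen depleting exercise will not be significantly different regardless of post-exercise recovery drink", the sample size in Section 17.2 rests on pilot TTE data, and TTE is named first in the analysis in Section 17.1. If expectancy came to differ by arm, part of any TTE difference between drinks would reflect belief rather than nutrition.

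**Working it through.** The plan gives no figure on this point to reproduce, so the check sets the sections side by side.

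**1. Order of events at Visit #3 (Sections 6.1, 6.4 and 6.7).** First interval and TTE bout; drink given; two hours of rest, with the survey at an unstated time within it; second interval and TTE bout; 30 minutes of HRV recording. Sections 6.1 and 6.7 agree, and nothing elsewhere moves the survey.

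**2. Gap between the survey and the second TTE (Section 6.4).**
- Intervals: 5 × 4 min = 20 min. Easy cycling between them: 4 × 2 min = 8 min. Total 28 min.
- Warm-up and rest: 3 + 2 + 1 + 3 = 9 min. With the intervals: 28 + 9 = 37 min.
- A survey finished at the end of the rest period precedes the TTE by about 37 min. One finished at its start precedes it by about 120 + 37 = 157 min. If the warm-up is not repeated, the range is about 28 to 148 min.

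The survey is therefore before the test, but not immediately before it.

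**3. When the survey could bias a contrast.** Let P(g|a) be the share of arm a who believe they had drink g, and s(g) the change in TTE that the survey adds among people with that belief. Assume that this change adds to any true drink effect. The mean shift in arm a is Σ P(g|a) × s(g), and the bias in, say, carbohydrate versus placebo is

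Σ [P(g|CHO) − P(g|PLA)] × s(g).

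- If masking is perfect, beliefs are distributed alike in every arm, each bracket is zero, and so is the bias. Variation in s(g) between people then adds only to residual variance.
- If masking is imperfect, the brackets are not zero, and any s(g) that depends on belief enters the contrast.

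The documents give neither the P(g|a) nor s(g), so no numerical value follows.

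**4. Whether the analysis removes it.** The ANCOVA in Section 17.1 adjusts for the pretest value. For TTE that comes from the first bout, before both drink and survey, so it cannot adjust for a shift that arises later.

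**5. Other safeguards.** None is specified: no masking check, no stated time for the survey within the two hours, and no reason given for the slot.

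**The case against.** The strongest reply is that all arms take the same survey, so its average effect cancels. That stands if masking holds. The survey creates a difference between arms only if participants can partly tell the drinks apart and the survey then acts on that. The documents show neither.

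Participants are also already primed. The study is explained at Visit #1, and the recruitment material in Section 13.3 sets out the objectives. Only what the survey adds to this counts, and that is unknown. The items cannot be seen, so whether any of them prompts guessing cannot be judged from the documents. These points limit the severity. They do not remove the concern, because masking is not checked and the exposure is easy to avoid.

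A reader might infer more in three ways that the documents do not support:

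- **A percentage bias or an inflated false-positive rate.** Multiplying an assumed share of correct guessers by an assumed expectancy effect, or assuming that both active arms are shifted, describes the whole consequence of failed masking. That would arise with no survey at all, so it does not measure what the survey adds.
- **A contaminated knowledge outcome.** The drink is masked, no teaching accompanies it, and the secondary objective describes the group as a whole, with no comparison between arms planned. No route is shown by which the drink would change knowledge.
- **A purposeless slot.** The documents give no reason for it, but using supervised rest time to secure complete answers is a legitimate choice.

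**Conclusion.** The point holds as a cheap improvement of low severity. It is established that the survey comes after the masked drink and before an effort-dependent test that supplies the main outcome, with no safeguard against cueing. It is plausible but not demonstrated that the survey strengthens expectancy. Bias between arms also requires imperfect masking of the whey drink or the placebo; without that, the most to expect is some added noise. The size cannot be estimated from the documents, and no sample size, alpha or power figure is affected. The conclusion rests on reading TTE as the main outcome and on the survey's subject as Section 6.7 describes it.

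**What to change.** Amend Sections 6.1 and 6.7 so that the survey is completed at Visit #3 after the second TTE and the 30-minute HRV recording, or electronically soon after the visit. Placing it after the HRV recording keeps that rest period undisturbed.

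The cost is a few extra minutes at the end of a visit that Section 9.1 puts at about 4 hours, with tired respondents. If it is done after the visit, a few surveys may be late or missing. No visit is added and the analysis is unchanged.

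Moving the survey to the window between Visits #2 and #3, alongside the ASA24 dietary recall, is a weaker option. Participants would still meet the same questions before the drink and the second ride, and the questions could influence the intake they report in the recall.
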